6. RANDOMIZATION

Subjects will be randomized 1:1 to receive either NTZ or placebo. An independent third party will prepare master randomization lists for each of the strata and maintain the masking of the study. Subjects who qualify for the study will be assigned to treatment using

centralized randomization procedures. The treatment numbers will appear on the bottles containing the masked study medication. The randomization list will be masked to study participants including Sponsor, Investigators, study monitors, statisticians, subjects and laboratory personnel. Unmasking procedures will be detailed in the Medical Monitoring Plan and Investigators will be provided instructions for unmasking.

7. DATA MANAGEMENT

7.1. Electronic Data Entry

Data will be transcribed from source documents into an electronic data capture (EDC) system.

The responsible study monitor(s) will verify data according to the Clinical Monitoring Plan, either remotely or at the clinical study site. The Investigator will ensure that the data recorded are accurate and complete.

Queries emerging during data cleaning will be generated within the EDC system by data management or clinical research associates. The Investigator or his/her designee will answer the queries and update the source data, if needed.

Adverse events and comorbid conditions will be coded by data management using the latest version of the Medical Dictionary for Regulatory Activities (MedDRA). Medications will be coded by data management using the World Health Organization (WHO) Drug Dictionary.

After the last subject's last visit has taken place, the database will be cleaned as necessary. As soon as the database is considered clean, it will be locked. The locked database will be used in the final statistical analysis for study reporting. Measures will be undertaken to protect subject data handled during inspections against disclosure to unauthorized third parties. Subject confidentiality will be maintained at all times.

7.2. Protocol Deviations

Protocol deviations will be documented by the Investigator, reported to the institutional review board (IRB) as appropriate, and also reviewed by the assigned clinical research associate. Deviations will be reported in the clinical trial management system or applicable EDC. Each deviation will be classified as major or minor according to the following definitions:

Major protocol deviation: A deviation that has an impact on subject safety, may substantially alter risks to subjects, may have an effect on the integrity of the study data, or may affect the subject's willingness to participate in the study

Minor protocol deviation: All other protocol deviations.

7.3. Data Quality Assurance

The accuracy and reliability of the study data will be assured by the selection of qualified Investigators and appropriate study centers, review of protocol procedures with the

Investigator and associated personnel prior to the study, and by periodic monitoring visits by the Sponsor or Sponsor's representatives. Written instructions will be provided for collection, preparation, and shipment of samples.

The monitor will review the source data for accuracy and completeness, and any discrepancies will be resolved with the Investigator or designee, as appropriate.

The Sponsor will be entitled to inspect and audit the facilities used in the clinical and laboratory parts of the study, as well as to make anonymized copies of all the data files pertaining to the study. Similar procedures may also be conducted by agents of any regulatory body, either as part of a national GCP compliance program or to review the results of this study in support of a regulatory submission. The Investigator should immediately notify the Sponsor if they have been contacted by a regulatory agency concerning an upcoming inspection.

8. STATISTICAL CONSIDERATIONS

8.1. Sample Size Calculations

For purposes of calculating our sample size, we assume that the proportion of subjects experiencing COVID-19 over a 6-week period is 1% and that the proportion of subjects experiencing any VRI is 2%. Current illness rates in the trial are approximately 1.2% for COVID-19 and 2.8% for VRIs. We further assume that effective prophylaxis will result in 80% reduction of the illness rate. Influenza prophylaxis studies of oseltamivir have resulted in approximately 80% reduction of influenza illness (see Tamiflu[®] prescribing information).

Using these assumptions, a Cox proportional hazards regression model (fitting the strata and treatment arm as a set of indicator variables) can be used to generate the number of events (COVID-19 cases) needed for 90% power to detect a hazard ratio of 0.8 versus a hazard ratio of 1. This number is 17 events. Earlier iterations of this protocol were sized on the assumption of a 3% overall rate for COVID-19 cases. Because the infection rate is much lower than anticipated, the Sponsor has decided to power the trial based on event counts. The intent is to keep the Cochran-Mantel-Haenszel (CMH) analysis previously planned. The expected sample size was generated from the event count required and the current illness rate approximating 1%. The power of the CMH analysis was then evaluated.

The expected sample size is 2842 subjects assigned equally to strata and to treatment arm within strata. This (fixed) sample size has 80.6% power for a CMH test of equal illness rates in the two treatment arms. When determining the fixed sample size necessary for 90% power for the CMH test under the current rates and effect size, a sample size of approximately 4000 is required. Under current assumptions this results in 23 expected events in the study – very near the number of events originally hypothesized based upon 800 total subjects and a blended illness rate of 3% for the two treatment arms.

A study-wide event count of 24 COVID-19 cases was chosen. This proposed event count results in power for the VRI endpoint (at the expected sample size) of 98.2%.

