4.2 Efficacy Analysis

4.2.1 Primary Efficacy Variables

This study has two primary endpoints: symptomatic COVID-19 disease and symptomatic VRI. The study-wise Type I error rate is 0.05, allocated $\alpha = 0.049$ to COVID-19 disease and $\alpha = 0.001$ to all VRI. In each case the hypotheses to be tested are

$$\begin{aligned}H_0: p_1 &= p_2 \\H_1: p_1 &\neq p_2,\end{aligned}$$

where p_1 represents the COVID-19 disease rate (or VRI rate) in the NTZ arm and p_2 represents the COVID-19 disease rate (or VRI rate) in the placebo arm.

Primary Analysis

The proportion of subjects experiencing symptomatic COVID-19 disease in the NTZ treatment group will be compared to the similar proportion in the placebo group using a two-sided CMH test with continuity correction at $\alpha=0.049$. The contingency tables will be provided with rates relative to the treatment margins. The common relative risk and the odds ratio between the treatment groups and 95% confidence intervals for these parameters will be provided. The analysis will be repeated by sex of subject (female or male), age group of subjects (18- 34 years, 35- 64 years, 65 years and older), and race of subject (white or non-white).

The proportion of subjects experiencing symptomatic VRI infections in the NTZ treatment group will be compared to the similar proportion in the placebo group using a two-sided CMH Chi-square test with continuity correction at $\alpha=0.001$. The contingency tables will be provided with rates relative to the treatment margins. The common relative risk and the odds ratio between the treatment groups and 95% confidence intervals for these parameters will be provided. The analysis will be repeated by sex of subject (female or male), age group of subjects (18- 34 years, 35- 64 years, 65 years and older), and race of subject (white or non-white).

While every effort will be made to compile the data in accordance with intent-to-treat, it is likely that some subjects will have missing endpoints. Subjects with missing outcomes data will be included in the primary analysis. The primary analysis will impute missing data as uninfected in each treatment arm. Best-case and worst-case sensitivity analyses will be performed as outlined in Section 2.3 above. In addition, a tipping point analysis will

be performed, imputing various levels of COVID-19 and VRI infection rates to missing values in the NTZ arm to determine the infection rate at which the study conclusions change.

Secondary Analysis

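### The Cox sample-size step states a hazard ratio of 0.8, but its 17 events correspond to a hazard ratio of 0.2 (the assumed 80% reduction); 0.8 would need about 844 to 849 events

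*Protocol*

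**What the plan says.** Protocol 8.1 sets a 6-week COVID-19 rate of 1% and then gives the treatment effect: "We further assume that effective prophylaxis will result in 80% reduction of the illness rate". From those assumptions a Cox model with indicators for stratum and arm is used to find the number of COVID-19 events "needed for 90% power to detect a hazard ratio of 0.8 versus a hazard ratio of 1". The result follows directly: "This number is 17 events".

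The section then turns the event count into subjects ("The expected sample size is 2842 subjects assigned equally to strata and to treatment arm within strata") and reports 80.6% power for the CMH test at that size. It gives about 4000 subjects for 90% CMH power, adding: "Under current assumptions this results in 23 expected events in the study". The target finally chosen is 24 COVID-19 cases.

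SAP 1.3 repeats the 80% reduction, the hazard ratio of 0.8 and the 17 events, and adds that the calculation was part of a blinded sample size re-estimation. The primary COVID-19 analysis in SAP 4.2.1 is a "two-sided CMH test with continuity correction" at alpha 0.049.

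**The concern.** The two statements of effect stand almost side by side and contradict each other. An 80% reduction leaves 20% of the hazard, a ratio of about 0.2. A ratio of 0.8 leaves 80% of it, a 20% reduction. Either the printed ratio or the event count had to be wrong, and the two cases differ greatly in consequence. If 0.8 were the intended effect, the event-driven design would be too small by a factor of about 50. If 0.2 were intended, the design stands and the text misdescribes it.

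In the second case what is at stake is interpretation. Read literally, the sentence claims 90% power for a 20% reduction. A non-significant result would then look like good evidence against even a modest benefit, which a trial of this size cannot supply.

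**Working it through.** **Inputs**
- Power 90%; stated hazard ratio 0.8; assumed reduction 80%; stated events 17 (Protocol 8.1, SAP 1.3).
- Allocation 1:1 (Protocol 6).
- Alpha: the Cox step gives neither alpha nor sidedness. I used two-sided 0.049, the level of the primary COVID-19 test, and two-sided 0.05, the study-wise level (SAP 4.2.1).
- COVID-19 rate 1% over 6 weeks, read as the placebo rate, so 0.2% on NTZ under an 80% reduction.

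**Step 1: the effect as a hazard ratio.** From 1% and 0.2%, HR = ln(1 − 0.002)/ln(1 − 0.01) = 0.199, in effect 0.2.

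**Step 2: events for 90% power.** Schoenfeld: d = 4(z₁₋α/₂ + z₀.₉₀)² / (ln HR)².

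At alpha 0.05, (1.960 + 1.282)² = 10.507, so 4 × 10.507 = 42.03. With (ln 0.2)² = 2.590, d = 42.03/2.590 = 16.23. With (ln 0.8)² = 0.04979, d = 42.03/0.04979 = 844.1.

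| | HR 0.2 | HR 0.8 |
|---|---|---|
| alpha 0.05, two-sided | 16.23 (17 events) | 844.1 (845 events) |
| alpha 0.049, two-sided | 16.31 (17 events) | 848.6 (849 events) |

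The plan's 17 is reproduced at 0.2 and not at 0.8. Inverting the formula, the ratio detectable with 17 events at 90% power is exp(−2 × 3.250/√17) = 0.207 (alpha 0.049). By the same formula, 17 events give 91.1% power at 0.2 and 6.6% at 0.8.

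**Step 3: other formulas.** At 0.8, one-sided Schoenfeld and Freedman counts run from 688 to 699, and two-sided Freedman gives 852 to 856. At 0.2, two-sided Freedman gives 24, one-sided Schoenfeld 14 and one-sided Freedman 20. No variant brings 0.8 near 17.

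**Step 4: the sample sizes.** The average rate over the two arms is (1% + 0.2%)/2 = 0.6% at a ratio of 0.2, and (1% + 0.8%)/2 = 0.9% at 0.8.

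| Subjects | Events at 1% vs 0.2% | Events at 1% vs 0.8% | Stated |
|---|---|---|---|
| 2842 | 17.05 | 25.6 | 17 |
| 4000 | 24.0 | 36.0 | 23 |

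In the other direction, 17/0.006 = 2833.3. Rounded up to a multiple of 14 (7 strata × 2 arms), this is 203 × 14 = 2842, the stated expected sample size.

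**Step 5: the CMH power figures.** A two-proportion approximation (alpha 0.049, no continuity correction, strata ignored) gives 78.6% at 2842 and 90.5% at 4000 for 1% versus 0.2%, near the stated 80.6% and 90%. For 1% versus 0.8% it gives 8.0% and 9.7%.

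**Step 6: what the planned test can detect.** Take exactly 24 events, 4000 subjects, the continuity correction and alpha 0.049, with strata ignored. The test is then significant in favour of NTZ with 6 or fewer NTZ cases. Given the total, NTZ cases are approximately binomial with share HR/(1 + HR): 0.167 at 0.2 and 0.444 at 0.8. Power in favour of NTZ is 90.9% at 0.2 and 4.1% at 0.8 (4.3% counting both tails). Simulation with 7 equal strata gives 90.9% and 4.3%.

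**The case against.** The strongest reply is that this is a labelling slip. The sentence opens by pointing back to the assumptions just stated, the 80% reduction is among them, and a careful reader can recover the intended ratio. Nothing operational rests on the printed value, and the 95% confidence intervals planned in SAP 4.2.1 would show how imprecise a null result is. All of this is true and limits the harm. It does not make the statement correct: the effect is misprinted in the power statement for the primary endpoint, in both documents.

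Four narrower points were considered.
- **Alpha, sidedness and formula are not given.** The figures of 17 and 844 to 849 are two-sided Schoenfeld counts. Other choices move them but leave hundreds of events at 0.8.
- **The 1% may be a pooled rate.** SAP 1.3 calls it study-wide. But a pooled 1% would reach 17 events at 17/0.01 = 1700 subjects, not 2842. Only the placebo-rate reading gives the plan's own number.
- **The 91% and 4% assume that 24 events are reached.** This stands as a condition. With enrolment capped at 4000 and 24.0 events expected, the chance of fewer than 24 is about 47%. These figures also describe the CMH test and not the Cox model, whose Schoenfeld power at 24 events and a ratio of 0.8 is 7.8%. Either way there is almost no power for a 20% reduction.
- **Other figures in the section may need attention.** The stated 23 events against 24.0 computed is a small mismatch, and the 98.2% power for VRI is a separate matter. Showing that 17 and 2842 fit a ratio of 0.2 does not vouch for these.

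**Conclusion.** The concern holds. The printed hazard ratio of 0.8 is wrong and the value behind the calculation is 0.2. The 17 events and the 2842 subjects follow from 0.2, and the figure of about 4000 is consistent with it. The error is a factor of about 50 in required events (17 against 844 to 849). The conclusion assumes 1:1 allocation, a two-sided Schoenfeld calculation at alpha 0.049 or 0.05, and 1% as the placebo rate. The first part, that 0.8 and 17 events are incompatible, survives every variant tried. This is an error of statement and not of design. It should be corrected because it misreports what the trial was powered to detect.

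**What to change.** In Protocol 8.1 and SAP 1.3, replace the hazard ratio of 0.8 with a hazard ratio of 0.2 (80% reduction). That is one phrase in each document. This correction leaves the 17 events, the sample sizes, the 24-event target, the alpha levels and the analysis unchanged. A statement of power for a 20% reduction is not needed to repair the error. If either document can no longer be amended, a dated clarification in the SAP or the study report would serve.

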8.4.1. Efficacy Analyses

Efficacy analyses will be based on a population consisting of all subjects randomized without a laboratory-detected viral respiratory infection at the baseline visit (intention-

to-treat or ITT population). All chi-square analyses will be calculated with appropriate continuity corrections.

There will be two primary efficacy analyses:

- The proportion of subjects experiencing COVID-19 in the NTZ treatment group will be compared to that of the placebo treatment group using a two-sided Cochran-Mantel-Haenszel (CMH) chi-square test ($\alpha = 0.049$).
- The proportion of subjects experiencing VRI in the NTZ treatment group will be compared to that of the placebo treatment group using a two-sided CMH chi-square test ($\alpha = 0.001$).

Secondary analyses will be performed as follows:

- The proportion of subjects experiencing COVID-19 or VRI for treatment vs control will be tested within strata using Pearson chi-square tests at an unadjusted $\alpha = 0.05$.
- Confidence intervals (95% confidence level) will be produced for the overall odds ratio and for the odds ratios for NTZ vs placebo for each stratum.
- Proportions of subjects experiencing mortality due to COVID-19 or complications thereof will be compared by treatment group using a two-sided Pearson chi-square test (unadjusted $\alpha = 0.05$).
- Proportions of subjects (with or without symptoms) testing positive for antibodies to SARS-CoV-2 at either of the Week 6 or Week 8 visits will be compared by treatment group using a two-sided Pearson chi-square test (unadjusted $\alpha = 0.05$).

Exploratory analyses will be performed as follows:

- Proportions of subjects experiencing each of the following will be compared by treatment group using a two-sided Pearson chi-square test (unadjusted $\alpha = 0.05$): (i) hospitalization due to VRI or complications thereof, (ii) mortality due to VRI or complications thereof, (iii) proportions of subjects experiencing acute respiratory illness (ARI), (vi) hospitalization due to ARI or complications thereof, (v) mortality due to ARI or complications thereof.

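### The 80.6% power given for 2842 subjects is not the power of the planned continuity-corrected CMH test, which is about 74.5% under the plan's own assumptions

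*Protocol*

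**What the plan says.** Protocol 8.1 assumes that "the proportion of subjects experiencing COVID-19 over a 6-week period is 1"% and that "effective prophylaxis will result in 80% reduction of the illness rate". It derives 17 events and, from those, a total size: "The expected sample size is 2842 subjects assigned equally to strata and to treatment arm within strata". It then gives the power at that size: "This (fixed) sample size has 80.6% power for a CMH test of equal illness rates in the two treatment arms". SAP 1.3 carries the same numbers. Neither section mentions a continuity correction.

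The same sections say that about 4000 subjects give 90% CMH power with 23 expected events, and they settle on 24 COVID-19 cases. The protocol synopsis allows 800 to 4,000 subjects to reach that count.

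The test itself is specified elsewhere. Protocol 8.4.1 sets a two-sided CMH test at alpha 0.049 for COVID-19 and adds: "All chi-square analyses will be calculated with appropriate continuity corrections". SAP 4.2.1 compares the NTZ proportion with that "in the placebo group using a two-sided CMH test with continuity correction".

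**The concern.** Protocol 8.1 says the CMH analysis already planned is being kept and that its power was then evaluated. A reader will take 80.6% as the power of the test that will be run. With about 17 expected events, a continuity correction is not a detail: it can move the result by a whole case in the split between arms. If 80.6% was computed without the correction, the power statement and the primary test do not match, and the chance of detecting the assumed effect at 2842 subjects is overstated.

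**Working it through.** **Inputs**
- n = 1421 per arm (2842 / 2; equivalently 7 strata x 2 arms x 203). Protocol 8.1; strata in SAP 1.1.
- Placebo rate p1 = 1% and NTZ rate p2 = 0.2% (80% reduction). Protocol 8.1.
- Two-sided alpha 0.049, so z = 1.9686 and z² = 3.875. Protocol 8.4.1, SAP 4.2.1.
- Continuity correction applied. Protocol 8.4.1, SAP 4.2.1.

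**Is 1% the placebo rate?** The average of 1% and 0.2% is 0.6%. 17 / 0.006 = 2833, and rounding up to fill 14 equal cells gives 14 x 203 = 2842. At 4000 subjects, 0.006 x 4000 = 24 events, close to the stated 23. Reading 1% as the placebo rate therefore reproduces the plan's own size. (The text also names a hazard ratio of 0.8. By Schoenfeld's formula 17 events match a ratio of 0.2, not 0.8, so the 80% reduction is used here.)

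**Trying to reproduce 80.6%: uncorrected test**
Power = Φ[(d − z·SE0) / SE1], with d = 0.008.
- SE0 = √(2 x 0.006 x 0.994 / 1421) = 0.002897
- SE1 = √((0.01 x 0.99 + 0.002 x 0.998) / 1421) = 0.002893
- (0.008 − 1.9686 x 0.002897) / 0.002893 = 0.794, so power = **78.6%**

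Exact enumeration of the two binomials, rejecting when (|x1 − m/2|)² / V > 3.875, gives **82.7%**. Here x1 is the placebo case count, m the total cases, T = 2842 and V = n²m(T − m) / [T²(T − 1)]. The stated 80.6% lies between the two uncorrected values and equals neither.

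**The planned test: corrected**
The correction replaces |x1 − m/2| by |x1 − m/2| − 0.5, which lowers d by 1/n = 0.000704.
- Normal approximation: (0.008 − 0.000704 − 0.005704) / 0.002893 = 0.550, so power = **70.9%**
- Exact enumeration: **74.5%**
- Simulation of the stratified test with 7 strata: 74.4%; between 1 and 7 strata the result stays within 74.4% to 74.6%

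**Why the gap is this large.** With 17 cases V = 4.226. A 13 to 4 split gives 4.5² / 4.226 = 4.79 uncorrected, which is significant. Corrected it gives 4.0² / 4.226 = 3.79, which is not. The corrected test needs 14 to 3.

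**Where the corrected test stands at other sizes**

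| Setting | Corrected | Uncorrected |
|---|---|---|
| 2842, exact | 74.5% | 82.7% |
| 2842, normal approximation | 70.9% | 78.6% |
| 3200, exact | 80.5% | 87.4% |
| 4000, exact | 89.8% | 93.7% |
| 4000, normal approximation | 86.5% | 90.5% |
| Given 24 events (placebo share 1/1.2 = 5/6) | 90.9% | 96.5% |

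By the exact calculation the corrected test reaches 80.6% only slightly above 3,200 subjects.

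**The case against.** **The input behind 80.6% may be the rate rather than the correction.** Protocol 8.1 also reports: "Current illness rates in the trial are approximately 1.2% for COVID-19 and 2.8% for VRIs". With a 1.2% placebo rate, the corrected test at 2842 has 79.9% by the normal approximation and 83.4% exact, which also surrounds 80.6%. This is the best alternative reading, and it means the cause cannot be proved. It does not fit the rest of the section. SAP 1.3 describes 1.2% as coming from blinded pooled data, so it is not a placebo rate. With 1.2% and 0.24% the average is 0.72%: 17 / 0.0072 = 2361, not 2842, and 0.0072 x 4000 = 28.8 events, not 23. Reading 1% as the pooled rate does not help either: corrected power at 2842 is then 94.7%, and 17 / 0.01 = 1700.

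**The 2842 is not the stopping point.** This stands. A reader might infer that the trial carries a one-in-four risk of missing a true 80% effect (100 − 74.5 = 25.5%, against 19.4% as printed). The documents do not support that: no planned efficacy rule ends enrolment at 2842 with about 17 events. Enrolment continues to 24 cases, and if these had accrued by 2842 subjects the corrected power would be 90.9%.

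**The pair of printed figures.** A reader might also infer that about 4000 for 90% is right for the corrected test while 80.6% is not, so that the loss from stopping early is misstated. That depends on the method. Corrected power at 4000 is 89.8% exact but 86.5% by the normal approximation. The uncorrected normal formula gives 78.6% at 2842 and needs 3934 for 90%, so on that basis the two printed figures roughly agree with each other.

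**Conclusion.** The point holds in a limited form. Under the plan's stated rates (1% and 0.2%), 1421 per arm and two-sided alpha 0.049, the planned continuity-corrected CMH test has about 74.5% power at 2842 subjects. The printed 80.6% is about 6 points above the exact value and about 10 points above the normal approximation. With those inputs it fits an uncorrected test only, but the sponsor's derivation is not documented, so omission of the correction is an inference and not a demonstrated slip.

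The conclusion rests on 1% being the placebo rate, which the 17 events and 2842 subjects support, and it does not depend on the number of strata. It does not show that the trial is underpowered. The choice of 24 events, with about 90% corrected power by the exact calculation, is if anything better justified by the lower figure at 2842.

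**What to change.** In Protocol 8.1 and SAP 1.3, do one of the following:
- replace 80.6% with about 74.5% for the continuity-corrected CMH test, stating the rates (1% and 0.2%), alpha 0.049 and the calculation method; or
- keep 80.6%, label it as the power of an uncorrected test if the sponsor's records confirm this, and print the corrected value beside it.

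Do not label the other power figures in these sections, including 98.2% for VRI, as corrected until they have been recomputed.

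The cost is one less favourable figure in two documents. The primary test, the alpha, the 24-event target and the 4,000 maximum do not change, and no extra subjects are needed.
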